Participants will keep a journal documenting how long they wore the mouthpiece at night and during the day, reasons for taking it out, and can make comments about the mouthpiece.

Exit questionnaires

Participants will complete an open-ended exit questionnaire regarding their experience with the mouthpiece and the Global Rate of Change Scale (GRC) after wearing the mouthpiece for one month.

Protocol

A phone screen will be used to screen for preliminary study suitability. If the potential participant passes the phone screen and would like to enroll in the study, we will then schedule them for their in-person visit.

The first visit will be in-person on the ground floor of the Movement Science Research Center at [name]. The study visit will follow the following schedule:

Informed consent, MMSE, nFOG (15 minutes): A trained researcher will review the informed consent document with the participant, outlining the study objectives and ensuring the participants have the opportunity to ask the researcher any questions they may have regarding the study and procedures. If the participant wants to continue, they will sign the consent form. The MMSE will be performed to screen for cognitive impairments which would affect study participation. The nFOG will provide us with information about freezing of gait if applicable.

Motor Assessment #1 without mouthpiece (45 minutes): MDS-UPDRS-III, GAITRite, Mini-Bestest (order will be randomized)

Dental Measurements (15 minutes): [name] will take dental measurements for the purpose of creating a custom-fitted mouthpiece as outlined in the Methods section.

Questionnaires, Medical History, Medications (30 minutes): The participants will complete demographic, medical history/medications forms, sleep and quality of life questionnaires while their mouthpiece is being fabricated.

Mouthpiece in (25 minutes): After their mouthpiece has been fabricated and adjusted (smoothed as needed), participants will sit with the mouthpiece in for 25 minutes.

Motor Assessment #2 with mouthpiece (45 minutes): MDS-UPDRS-III, GAITRite, Mini-Bestest, (order will be randomized)

Participants who take medication for Parkinson symptoms, will be asked to take their medication 30 minutes before arrival to ensure participants are in the "on" phase for the motor tasks.

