At completion of the in-person visit, participants will be instructed to use the mouthpiece as much as possible for the next month. Participants will be informed they can take the mouthpiece out while eating and will be instructed to keep track of how long they wear the mouthpiece each day by journal entry.

Follow-up will occur one month later.

Questionnaires, Medical History, Medications (30 minutes): The participants will complete sleep and quality of life questionnaires, record any changes in their medical history or medications, and complete an open-ended questionnaire regarding their thoughts on the mouthpiece and the GRC.

Randomization Method

The order in which the motor assessments are given in regards to wearing the mouthpiece or not will be randomized for each participant. The motor tasks (disease severity, gait, balance) will be randomized within each participant.

Safety and Adverse Events

The research team will do everything possible to ensure safety of all participants over the course of this study. The adverse event most likely to occur in this study is risk of falling while walking. Participants will be fitted with a gait belt. Members of the research team are trained in fall prevention and will closely monitor all participants throughout all aspects of the study in case of a need to assist with balance to prevent a fall. In the case of an adverse event, emergency medical care will be sought immediately if needed. Any serious adverse events will be reported to the local IRB immediately. Occurrence of an adverse event will be noted in a participant's file.

Potential risks will be addressed in the following ways:

- a) Discomfort in answering questionnaires: Participants may refuse to answer any questions they prefer not to answer.
- b) Loss of confidentiality: Loss of confidentiality is highly unlikely. To safeguard against this, we will comply with all HIPAA regulations. Data will not be identified by participant name. All data will be coded, and code sheets will be stored in locked files.
- c) Stumbling during locomotion: Participants will be closely attended by a trained research staff member during walking and fitted with a gait belt. Walking will be performed in a large, open space and the staff member will be prepared to assist participants who may stumble.

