- d) Falling: Participants will be closely attended by a trained assistant who will ensure the safest of conditions. It is unlikely that participants will experience falls during testing or will be injured as the result of a fall. If a participant appears unsteady, breaks will be encouraged or testing will be terminated.
- e) Fatigue from walking: Rest breaks will be provided as needed.

Dental Appliance for Parkinson Disease (DAPD)

f) Discomfort or irritation while being fitted for the mouthpiece or while wearing the mouthpiece: the participants may remove the mouthpiece at any time.

Benefits

We do not yet know the full extent to which the mouthpiece may improve symptoms associated with Parkinson disease. This study may help inform future treatment techniques to improve motor and non-motor function in people with PD.

Interim Monitoring and Early Stopping

Data will be monitored throughout the study and, should any issues arise, we will adjust our protocol and submit any changes to the IRB project for review. We will not conduct interim data analyses.

Statistical Analyses Plan

We will use paired t-tests to determine if there are differences between conditions (with mouthpiece vs without mouthpiece). We will also use paired t-tests to compare sleep and quality of life questionnaires from baseline (prior to study) to follow up (after one month of mouthpiece use).

R will be used for data analysis across all aims.

Power

Because of the exploratory nature of this pilot study and relative lack of information in the literature, no formal power analysis was conducted.

References:

- 2. Shulman LM. Understanding disability in Parkinson's disease. Mov Disord 2010;25 Suppl 1:S131-5.
- 4. Ellis TD C, JT, Earhart GM, Ford MP, Foreman KB, Thackeray A, Thiese MS, Dibble LE. Identifying clinical measures that most accurately reflect the progression of disability in Parkinson disease. Parkinsonism Relat Disord 2016;25:65-71.

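### Aim 1: the protocol gives both a randomised and a fixed mouthpiece order, and the paired t-test takes no account of order under either

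*Combined protocol and SAP*

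**What the plan says.** Three places bear on this.

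- **Statistical Analyses Plan.** "We will use paired t-tests to determine if there are differences between conditions (with mouthpiece vs without mouthpiece". No order, period or sequence term appears there or elsewhere.
- **Randomization Method.** "The order in which the motor assessments are given in regards to wearing the mouthpiece or not will be randomized for each participant". A separate sentence covers the tests: "The motor tasks (disease severity, gait, balance) will be randomized within each participant".
- **Protocol (visit schedule).** It opens with "The study visit will follow the following schedule" and lists a single sequence: "Motor Assessment #1 without mouthpiece (45 minutes): MDS-UPDRS-III, GAITRite, Mini-Bestest (order will be randomized"; then dental measurements, questionnaires during fabrication, and 25 minutes seated with the mouthpiece in; then "Motor Assessment #2 with mouthpiece (45 minutes". No schedule is given for a visit that starts with the mouthpiece.

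The remark about randomised order in the schedule follows the list of three tests. It therefore matches the sentence on motor tasks, not the one on wearing the mouthpiece, and does not resolve the conflict.

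Participants on Parkinson medication "will be asked to take their medication 30 minutes before arrival". On sample size the document says only that "no formal power analysis was conducted".

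**The concern.** Aim 1 asks for the immediate effect of the mouthpiece on gait and motor symptoms. Each participant does the same three tests twice in one long visit, so the second set may differ from the first whatever is in the mouth: better through practice, worse through fatigue, or either way as medication effect changes. Whether the comparison can separate this from the mouthpiece depends on the order rule, and the document gives two.

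Under the fixed schedule, a significant difference could be practice, and a null result could be fatigue or time since medication hiding a benefit. Under randomised order the comparison is sound, but the planned test ignores the factor that was randomised. Any order effect then goes into the error term and, when the split is uneven, partly into the estimate.

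**Working it through.** **Timing.** From the visit schedule, steps run back to back:

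- Assessment #1 starts 15 minutes after arrival (consent, MMSE, nFOG).
- Assessment #2 starts at 15 + 45 + 15 + 30 + 25 = 130 minutes.
- Gap: 130 − 15 = 115 minutes.
- For medicated participants, add 30: 45 and 160 minutes after the dose.

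An order effect is therefore plausible. The documents do not quantify it.

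**Model.** Let d be a participant's with-minus-without difference, in units of its SD:

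d = τ + π·s + e, with s = +1 if the mouthpiece is worn second and −1 if first.

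Here τ is the mouthpiece effect and π the mean second-minus-first change. The document states no figure to reproduce. Assumed: n = 12, 20, 30; π = 0 to 0.8; τ = 0 or 0.6; two-sided 5% level; no carryover.

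**Fixed order.** Every s is +1, so the design matrix [1, s] has rank 1 of 2. Only τ + π can be estimated, and no model can separate the two. With τ = 0 the paired t-test follows a noncentral t with noncentrality π√n:

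| n | π | π√n | Rejects with no mouthpiece effect |
|---|---|---|---|
| 12 | 0.3 | 1.04 | 16% |
| 12 | 0.5 | 1.73 | 35% |
| 20 | 0.3 | 1.34 | 25% |
| 20 | 0.5 | 2.24 | 56% |

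**Randomised order.** The matrix has rank 2, so π can be estimated. The paired t-test uses the mean of all d with n − 1 df. The order-adjusted test uses the mean of the two sequence means with pooled variance and n − 2 df. Results below are from 200,000 simulated trials per cell.

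*Balanced orders, τ = 0.6: power, paired t v adjusted*

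| n | π = 0.3 | π = 0.5 | π = 0.8 |
|---|---|---|---|
| 12 | 44 v 47% | 38 v 47% | 26 v 47% |
| 20 | 69 v 72% | 63 v 72% | 50 v 72% |
| 30 | 87 v 89% | 83 v 89% | 74 v 89% |

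At π = 0 the two agree to about one point. At n = 20 the mean 95% interval width is 0.97 v 0.93 SD (π = 0.3) and 1.04 v 0.93 SD (π = 0.5).

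*Unblocked simple randomisation, τ = 0.6.* With no order effect, adjusting costs power: 47 v 43% (n = 12), 72 v 70% (n = 20), 89 v 88% (n = 30). At π = 0.3 the two are about equal. At π = 0.5 adjusting gains: 39 v 43% (n = 12), 62 v 70% (n = 20). With τ = 0, both tests average 5% type I error.

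*Conditional on the realised split.* With n1 participants wearing the mouthpiece second and n2 first, the paired estimate shifts by π(n1 − n2)/n. At 14:6 and π = 0.5 this is 0.5 × 8/20 = 0.2 SD. At n = 20 and π = 0.5, the type I error of the paired t-test is 2.9% at 10:10, 4.5% at 12:8, 6.6% at 13:7 and 9.8% at 14:6. The adjusted test stays at 5%. From Binomial(20, 0.5), the chance of a split of 13:7 or worse is 26%, and of 14:6 or worse 11.5%.

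**The case against.** The paired t-test is not itself an error. Under simple randomisation it is unbiased with 5% type I error, and under fixed order nothing better exists. The real defect is then the contradiction over order, and the missing term is secondary. That is right, and it is why reconciliation comes first.

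The protocol mentions no blocking, so simple randomisation is the natural reading. Adjustment then loses or ties until the order effect passes about 0.3 SD. This stands, so the order term should come with a blocked list.

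Every size above rests on assumed inputs, in an exploratory pilot with no power target. This also stands. The protocol's rest breaks may reduce fatigue, and the medication timing applies only to those who take it.

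The strongest practical objection is timing. On the stated durations, a mouthpiece-first visit cannot start its first assessment before 15 + 15 + 30 + 25 = 85 minutes, against 15 minutes for the other order. The gap to the second assessment would be 45 minutes instead of 115. If the order effect scaled with the gap, π would be 0.5 in one sequence and 0.5 × 45/115 = 0.20 in the other. The adjusted estimate would then be off by (0.50 − 0.20)/2 = 0.15 SD, with type I error near 10% (n = 20, balanced). Matched timing is therefore a condition of the fix.

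Carryover is also assumed away. If a fraction c of the effect persists after removal, the two sequences average τ and τ(1 − c), so the estimate falls to τ(1 − c/2): three quarters of τ at c = 0.5. No washout is described. This has to be stated as an assumption.

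**Conclusion.** The concern holds. The visit schedule and the Randomization Method section contradict each other on condition order, and the planned test takes no account of order under either.

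The fixed-order reading is the serious one: the whole order effect enters the Aim 1 estimate and cannot be removed. Under randomised order there is no bias on average. The cost is precision, about 3 power points at a 0.3 SD order effect and 9 at 0.5 SD (n = 20, balanced, 0.6 SD effect), plus a shifted estimate when the split is uneven. In a pilot this matters mainly for the width of the interval carried into a later trial.

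The contradiction and the confounding follow from the text alone. The sizes depend on assumed values for n, the mouthpiece effect and the order effect. The point should be settled before analysis.

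**What to change.** 1. **Reconcile the two sections** and state which order rule applies.
2. **If order is randomised:**
   - Assign the two orders from a blocked 1:1 list.
   - Write the visit schedule for both orders, with matched timing of the two assessments.
   - Replace the Aim 1 sentence with, for example: *Gait velocity and Mini-BESTest (and MDS-UPDRS-III, if it is to be compared between conditions) will each be analysed with a two-period crossover model, with condition and period as fixed effects and participant as random effect. The condition effect will be reported with a 95% CI, assuming no differential carryover.*
   - In R, an equivalent with complete pairs regresses d on sequence with sum-to-zero coding (`contr.sum`), so that the intercept is the condition effect. Default coding returns one sequence's mean instead: with τ = 0.6 and π = 0.5 that can be 0.6 − 0.5 = 0.1.
   - The paired t-test can stay as a supportive check.
3. **If order is fixed:** keep the paired t-test, fit no order term, and state that the difference is confounded with assessment order and cannot be attributed to the mouthpiece.

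**Cost.** On paper: one sentence on order, revised SAP wording, a blocked list and one degree of freedom. In the clinic, randomised order needs the mouthpiece made before the first assessment in mouthpiece-first visits, and the other visits retimed to match. Adjusting without blocking, when there is no order effect, loses about 4 power points at n = 12 and 2 to 3 at n = 20, so the model and the list should be adopted together. Fixed order costs nothing to run but limits what Aim 1 can conclude.
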